92147168, Rev/Ver C	May 17, 2018	Template 90702637 Rev/Ver AH	Study Objective, Synopsis, Exclusion Criteria 5, 6, 7, 8, 16, 5.2	Added statement to Study Objective, Changed Exclusion Criteria # 9; add collection of current medications at baseline and follow-up visits and exclude patients with any prior interventions; change follow-up of patients who do not have an AXIOS stent implanted; change primary analysis cohort and enrollment cohort to ITT; specify the evaluation of the primary effectiveness endpoint; minor edits to section 7.4 to match synopsis; added exclusion criterion. Added windows for end of study visit and 72hr post stent removal visit; raised the number of participating centers	Per FDA review and feedback
92147168, Rev/Ver D	August 15, 2018	Template 90702637 Rev/Ver AJ	Synopsis, Section 7, 17, 18, 20, 21	Updated language to reflect updated protocol template	Updated protocol template

Revision Number	Release Date	Template number and version	Section	Change	Reason for Change
92147168, Rev/Ver E	September 05, 2018	Template 90702637 Rev/Ver AJ	Synopsis, Section 5.1, Figure 4.3-1, 8.1	Updated inclusion criteria #2 in Synopsis and Section 5.1; updated flowchart in Figure 4.3-1; added that patient not receiving an Axios stent will be censored in the KM analysis at 60 days. Added a sensitivity analysis for the KM analysis; updated number of centers in synopsis	Per FDA review and feedback
92147168, Rev/Ver F	October 18, 2018	Template 90702637 Rev/Ver AJ	Synopsis, Section 4.1; Contact information	Updated primary effectiveness endpoint in synopsis and section 8.1; Changed sample size to 24 patients; Updated coordinating lead investigator	Per FDA review and feedback
92147168, Rev/Ver G	November 6, 2018	Template 90702637 Rev/Ver AJ	Synopsis, Section 4.1;	Updated primary effectiveness endpoint in synopsis and section 8.1; Changed sample size to 30 patients; updated number of centers in the synopsis	Per FDA review and feedback
92147168, Rev/Ver H	December 19, 2018	Template 90702637 Rev/Ver AJ	Additional Endpoints, Section 8.1, Section 16.1	Updated Additional Endpoints and section 8.1; Changed performance goal to 3.5 days. Section 16.1 edited to reflect coverage of Adverse Events and Adverse Device Effects	Per FDA review and feedback

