The primary effectiveness endpoint will be evaluated for all ITT patients regardless of whether an AXIOS™ stent is implanted. Patients for whom an AXIOS™ stent is implanted and cholecystitis is resolved will be considered a success for the endpoint and the days to resolution will be the date of resolution minus the date of the index procedure. If a patient does not receive an AXIOS™ stent, the patient will be considered a failure for the endpoint with censoring at 60 days. If a subject receiving an AXIOS™ stent does not achieve resolution of cholecystitis for any reason, the patient will be treated as censored in the Kaplan-Meier analysis and the days to censoring will be the date of censoring minus the date of the index procedure. The date of censoring will be the earliest of the following:

- date of the patient receiving a cholecystectomy,
- date of the patient dying,
- date of last contact for patients who withdraw from the study or are lost to follow-up, or
- date of the AXIOS™ stent removal.

Success Criteria for the Primary Effectiveness Endpoint:

For the primary effectiveness endpoint of days to clinical resolution, testing will be performed as described below.

The mean time to resolution and standard error of the mean will be estimated from a Kaplan-Meier analysis so that subjects for whom resolution is not obtained can be included in the analysis.

The estimated mean and standard error from the Kaplan-Meier analysis will be used to construct a one-sided 97.8% upper confidence bound of the mean. If the upper 97.8% confidence bound of the mean days to clinical resolution for the AXIOS™ group is less than the performance goal of 3.5 days, the null hypothesis will be rejected in favor of the alternative hypothesis and the mean days to resolution for the AXIOS™ group will be considered to be significantly less than the performance goal of 3.5 days.

As a worst-case scenario sensitivity analysis, the Kaplan-Meier analysis for the primary effectiveness endpoint will be re-analyzed with 60 days as the time to censoring for all censored patients with time to censoring <60 days.

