2. INTRODUCTION

This statistical plan addresses the planned analyses for the Axios Gallbladder Drainage IDE Study based on protocol # 92147168. Specified analyses may be used for scientific presentations and/or manuscripts and may not all be provided to Regulatory Authorities.

IMPORTANT NOTE: This SAP documents changes to the Statistical Methods outlined in the protocol. This SAP shall be following where there are any differences between the Statistical Methods in the protocol and this SAP. *Differences to the Statistical Methods between the protocol and this SAP will be in bold, italics.*

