3.1.2 Sample Size Calculation

This analysis of the primary effectiveness endpoint is to compare the observed days to clinical resolution for AXIOS™ stents from this study to a PG.

- Expected AXIOS™ stent (test) mean days to clinical resolution = 2.35 days with standard deviation 2 days (point estimate of days to clinical resolution based on historical rates reported in literature [1] with median days to clinical response of 1 day, range 0 to 3 days)
- PG = 3.5 days (mean days to resolution for percutaneous gallbladder (GB) drainage (PC-GBD) based on historical rates reported in literature [2])
- Test significance level (α) = **0.025** (1-sided)
- Power (1- β) = **82%**
- Evaluable number of patients needed = 27
- Expected rate of attrition = 10%
- Enrolled number of patients = 30

The historical time to cholecystitis resolutions comes from 2 studies that report time to cholecystitis for endoscopic ultrasound-guided transmural gallbladder drainage (EUS-GBD) [1] and PC-GBD [2] (Table 3.1-1).

Table 3.1-1. Time to Cholecystitis Resolution (in days)

Reference	EUS-GBD	PC-GBD
Irani (2015) [1]	Median=1 (0-3) [N=15]	N/A
Kedia (2015) [2]	N/A*	Mean 4.6 [N=43]

* Endoscopic drainage was not transmural and therefore was not included in the analysis

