3.1.3 Analysis

The primary effectiveness endpoint will be evaluated for all ITT patients regardless of whether an AXIOS™ stent is implanted. Patients for whom an AXIOS™ stent is implanted and cholecystitis is resolved will be considered a success for the endpoint and the days to resolution will be the date of resolution minus the date of the index procedure. If a patient does not receive an AXIOS™ stent, the patient will be considered a failure for the endpoint with censoring at 60 days. If a subject receiving an AXIOS™ stent does not achieve resolution of cholecystitis for any reason, the patient will be treated as censored in the Kaplan-Meier analysis and the days to censoring will be the date of censoring minus the date of the index procedure. The date of censoring will be the earliest of the following:

- date of the patient receiving a cholecystectomy,
- date of the patient dying,
- date of last contact for patients who withdraw from the study or are lost to follow-up, or
- date of the AXIOS™ stent removal.

The mean time to resolution and standard error of the mean will be estimated from a Kaplan-Meier analysis so that subjects for whom resolution is not obtained can be included in the analysis.

The estimated mean, $\hat{\mu}_T$, from the Kaplan-Meier analysis will be calculated as:

$$\hat{\mu}_T = \int_0^T \hat{S}(t)dt$$

where $\hat{S}(t)$ is the estimated survival function from the Kaplan-Meier analysis and T is time of longest days to resolution or days to censoring. The variance of $\hat{\mu}_T$, $\hat{V}(\hat{\mu}_T)$, is estimated as:

$$\hat{V}(\hat{\mu}_T) = \sum_{i=1}^D \left[\int_{t_i}^T \hat{S}(t)dt \right]^2 \frac{d_i}{Y_i(Y_i - d_i)}$$

where D is the number of distinct times (days to resolution), t_i is the i-th time, Y_i is the number of patients at risk at time t_i , and d_i is the number of events at time t_i . The $100(1 - \alpha)\%$ upper bound of the confidence interval of the mean will be calculated as:

$$\hat{\mu}_T + Z_{1-\alpha} \sqrt{\hat{V}(\hat{\mu}_T)}$$

For the primary effectiveness endpoint of days to clinical resolution, testing will be performed as described below.

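### The stated 82% power leaves out the 60-day rule: with 30 patients, one ITT patient without a stent makes the 3.5-day goal unreachable

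*SAP*

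**What the plan says.** The primary analysis covers the whole ITT cohort. Protocol 8.1 states: "The primary effectiveness endpoint will be evaluated for all ITT patients regardless of whether an AXIOS™ stent is implanted", and SAP 3.1.3 agrees. For failed placement both say: "If a patient does not receive an AXIOS™ stent, the patient will be considered a failure for the endpoint with censoring at 60 days". The mean is the area under the Kaplan-Meier curve from 0 to T, where "T is time of longest days to resolution or days to censoring". Success requires the one-sided upper confidence bound of that mean to lie below 3.5 days. The bound is 97.5% in the SAP and 97.8% in the protocol, and the SAP prevails: "This SAP shall be following where there are any differences between the Statistical Methods in the protocol and this SAP".

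SAP 3.1.2 takes its power from "Expected AXIOS™ stent (test) mean days to clinical resolution = 2.35 days with standard deviation 2 days", one-sided alpha 0.025 and 27 evaluable patients, and states 82%. It then adds "Expected rate of attrition = 10" per cent to reach 30. Protocol 8.1 uses the same inputs with alpha 0.022 and states 80.4%. Neither document lists a placement rate among the inputs.

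The protocol foresees failed placement: the synopsis and section 7.4 set out follow-up for patients in whom placement is attempted but no stent is left. According to the protocol revision history, Rev E "added that patient not receiving an Axios stent will be censored in the KM analysis at 60 days". The sample size of 30 came later (Rev G), as did the 3.5-day goal (Rev H).

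**The concern.** The power calculation describes patients who all receive a stent and resolve, on average, in 2.35 days. The analysis describes every patient in whom the procedure was begun, and gives each non-stented one a value of 60 days. Against a goal of 3.5 days and only 30 patients, a single 60 may decide the result whatever the other 29 show. If so, the stated power does not belong to the planned test.

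The cohort definition then carries unusual weight. Exclusion criterion 10 (distance between the gallbladder and the gastric or duodenal wall) is checked at the time of drainage, and Protocol 7.3 warns that EUS may show a patient to be unsuitable. Under Protocol 6.1 such a patient is a screen failure and is excluded. Under Protocol 6.4 and SAP 4.2 the same patient is in the ITT cohort once the endoscopic procedure has started. That one classification could settle the primary endpoint.

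**Working it through.** **1. The plan's own figure.** One-sample, one-sided t test, n = 27, difference 3.5 − 2.35 = 1.15, SD 2: power is 82.0% at alpha 0.025 and 80.4% at alpha 0.022. Both stated figures are reproduced. Attrition: 27/(1 − 0.10) = 30.

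**2. One non-stented patient, best case.** Take n = 30, with 29 resolving on day 0 and one censored at day 60, so T = 60 and the curve stays at 1/30 from day 0.
- Mean = 60 × 1/30 = 2.00 days.
- Variance (SAP 3.1.3) = 2.00² × 29/(30 × 1) = 3.87; SE = 1.966.
- 97.5% bound = 2.00 + 1.96 × 1.966 = **5.85 days** (97.8% bound: 5.96).

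A random search over 20,000 other patterns for the 29 patients found no lower bound. If all 29 resolve at the planned 2.35 days, the mean alone is (29 × 2.35 + 60)/30 = 4.27 and the bound about 8.0. The best-case bound is 6.50 at n = 27, 3.53 at n = 50 and 3.46 at n = 51, the first n at which one such patient could be absorbed.

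**3. Ceiling on power.** If each ITT patient receives a stent independently with probability p, then power = p³⁰ × (power when all 30 are stented). The second factor is at most 1, so p³⁰ is a ceiling for any distribution of resolution times.

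**4. Power when all are stented.** Whole-day (negative binomial) times with mean 2.35 and SD 2, analysed by the SAP formula at n = 30, give 0.848. Other shapes give 83% (gamma, lognormal) to 88% (normal).

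**5. Results at n = 30, all stented patients resolving.**

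| Assumed placement rate | Source | Ceiling p³⁰ | × 0.848 | Direct simulation |
|---|---|---|---|---|
| 100% | none failed | 100% | 85% | 84.8% |
| 98.7% | 74/75, one series, Appendix 24.1 | 66.9% | 56.7% | 56.2% |
| 96.6% | 141/146, Appendix 24.2 | 35.2% | 29.8% | 29.2% |
| 95.5% | 252/264, Appendix 24.1 (21 patients counted twice) | 24.8% | 21.0% | 20.0% |

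For even the ceiling to reach 82%, placement must be at least 0.82^(1/30) = 99.34%. For the power itself to reach it, (0.82/0.848)^(1/30), or about 99.9%.

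**6. A faster device does not help.** The source of the expected time reports "Median=1 (0-3) [N=15"]. Times of 0 to 3 days with median 1 and mean 1.35 give 100%, 67%, 35% and 25% at the four rates, which is the ceiling. The largest mean that source allows, (8 × 1 + 7 × 3)/15 = 1.93, gives the same to within about a point.

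**7. Stented patients who never resolve.** These lower power further, by an amount that depends on when they are censored. The documents do not fix that day, because the 30–60 day removal visit is tied to resolved cholecystitis. In the best case, one such patient among 30 gives a bound of 3.41 if censored on day 35 and 3.51 on day 36, so from day 36 success is again impossible. With exactly one such patient and the planned mean and SD for the rest, the trial passes 77%, 66%, 27% and under 1% of the time for assumed censoring on days 3, 7, 14 and 21.

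**The case against.** The 82% is arithmetically right for its inputs. The 60-day rule is a deliberate, conservative choice made during regulatory review; it does not inflate type I error, and the risk falls on the sponsor. That is true, and it is why the rule need not change. It does not make 82% the power of the planned analysis.

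The placement rates are the weakest input. Technical success is not the same as receiving a stent: the trial's own definition also needs confirmed patency, the series behind the sample size shows 14/15 technical but 15/15 clinical success, and one study in the 96.6% average may not have used this device. Selection criteria and the permitted second attempt could raise placement. Exact 95% limits are wide: 92.8–99.97% for 74/75 (ceiling 11–99%), 92.2–98.9% for 141/146 (ceiling at most 71%) and 92.2–97.6% for 252/264 (at most 49%). So 82% is not excluded by the most favourable series alone. The 57% and 30% must be read as conditional. The one-patient result needs no rate.

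The 85% refers to 30 patients and the stated 82% to 27. At n = 27 the figures are 80–85%, 57–60% and 32–34%, so the conclusion is the same. If software stopped the integral at the last resolution, power would be about 78% and 68% at 98.7% and 96.6%, but the SAP defines T to include censoring times.

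The Treated-cohort analysis will show the results in stented patients, but it is not the primary test. On the cohort, Protocol 6.4 and SAP 4.2 agree with each other, and the per-protocol definition implies that ineligible patients can be in ITT. Protocol 6.1 still says the opposite. The censoring days in step 7 are illustrative only.

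**Conclusion.** The point holds, and the power statement must be corrected. With 30 patients and the SAP's definition of T, one ITT patient without a stent rules out success on the primary endpoint, and therefore overall study success under SAP 3.3. This follows from the formula alone.

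The stated 82% is close to the truth only if essentially every patient is stented. Under the plan's mean and SD, with all stented patients resolving and placements independent, power falls from about 85% to 57%, 30% or 21% at assumed placement rates of 98.7%, 96.6% or 95.5%. The attrition allowance gives no cover, because non-stented patients stay in the analysis and count towards the 30. The conflict over patients found ineligible during the procedure is real, and one such classification can decide the result.

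**What to change.** 1. In SAP 3.1.2 and Protocol 8.1, keep the 60-day rule and replace the stated power with a simulation of the planned ITT Kaplan-Meier analysis. Cover placement rates of about 95% to 100%, with and without stented patients who never resolve, and state the censoring days assumed for them.
2. Before data are seen, reconcile Protocol 6.1 with Protocol 6.4 and SAP 4.2 on whether a patient found ineligible at EUS after the procedure has started is a screen failure or an ITT patient.

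The cost is a short simulation, an amended SAP, and a protocol revision of 6.1/6.4 and 8.1 with its approvals. The test, the goal and the number of patients do not change. The drawback is that the stated power will fall, to well under 80% at the placement rates in the appendices. The sensitivity to a single patient also remains: these changes disclose it and settle the classification in advance, but do not remove it.

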The estimated mean and standard error from the Kaplan-Meier analysis will be used to construct a one-sided **97.5%** upper confidence bound of the mean. If the upper **97.5%** confidence bound of the mean days to clinical resolution for the AXIOS™ group is less than the performance goal of 3.5 days, the null hypothesis will be rejected in favor of the alternative hypothesis and the mean days to resolution for the AXIOS™ group will be considered to be significantly less than the performance goal of 3.5 days.

As a worst-case scenario sensitivity analysis, the Kaplan-Meier analysis for the primary effectiveness endpoint will be re-analyzed with 60 days as the time to censoring for all censored patients with time to censoring <60 days.

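### The 82% power for the primary test assumes that every patient resolves; under the planned Kaplan-Meier rules one unstented patient fails the test, and the weight of a stented failure depends on its censoring date.

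*SAP*

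**What the plan says.** SAP 3.1.2 plans the primary test on an expected mean of 2.35 days, SD 2, a goal of 3.5 days and one-sided alpha 0.025. It states 82% power with 27 evaluable patients and enrols 30 to allow for 10% attrition. It gives no failure rate.

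SAP 3.1.3 analyses all ITT patients, with or without a stent, and treats non-resolution in two ways:

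- Unstented: "If a patient does not receive an AXIOS™ stent, the patient will be considered a failure for the endpoint with censoring at 60 days".
- Stented: "If a subject receiving an AXIOS™ stent does not achieve resolution of cholecystitis for any reason, the patient will be treated as censored". The date is the earliest of "date of the patient receiving a cholecystectomy", "date of the patient dying", last contact for withdrawal or loss to follow-up, and "date of the AXIOS™ stent removal".

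Protocol 8.1 has the same rule. The mean is the area under the Kaplan-Meier curve up to T, where "T is time of longest days to resolution or days to censoring". Success needs the upper 97.5% bound of that mean to lie below 3.5 days. A sensitivity analysis outside the success rule is "re-analyzed with 60 days as the time to censoring for all censored patients with time to censoring <60 days". SAP 3.2.3 plans a tipping-point analysis for the secondary endpoint; none is planned for the primary.

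**The concern.** The power figure and the analysis describe different things. A patient who never resolves does not drop out of the ITT analysis, so the 10% attrition allowance does not cover that patient. Because the mean is integrated to the longest observed time, one long censored time can dominate both the mean and its standard error.

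The weight of a stented failure also depends on when censoring falls. If it falls while others are unresolved, Kaplan-Meier in effect lets the patient resolve later as they do. If it falls after everyone else has resolved, the curve stays flat above zero up to that date and the whole interval counts. Early removal is foreseeable, since Protocol 7.4 has a misplaced or migrated stent removed.

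At stake is whether the sponsor knows the real chance of meeting the primary criterion with 30 patients, and whether a reader could tell a robust success from one that hangs on a single date.

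**Working it through.** **1. The plan's own figure.** Inputs from SAP 3.1.2: n = 27, difference 3.5 - 2.35 = 1.15, SD 2, one-sided alpha 0.025. Noncentrality = 1.15 / (2/√27) = 2.99, with 26 degrees of freedom and critical t 2.056. Power is 82.0%, as stated. At alpha 0.022 the same formula gives the protocol's 80.4%. Attrition: 27/0.9 = 30. The arithmetic is right, but the model has no failures and no censoring.

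**2. One unstented patient, most favourable case.** Let 29 of 30 resolve on day 0 and one be censored on day c. After day 0 the curve is 1/30, so:

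- mean = c/30
- variance = (c/30)² × 29/(30 × 1)
- bound = (c/30) × (1 + 1.96 × √(29/30)) = 0.0976c

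For c = 60 the mean is 2.00, the standard error 1.97 and the bound 5.85. If all 29 others resolve on day 1 the bound is 6.76, and on day 2 it is 7.66. So one patient held to day 60 fails the test. In this best case the bound is 3.41 at c = 35 (pass) and 3.51 at c = 36 (fail).

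**3. Success by unstented rate.** Since any unstented patient fails the test, success is about (1 - p)^30 times the success rate without failures. The latter is about 83% in simulation of the SAP formulas (n = 30, gamma times, mean 2.35, SD 2; separate runs gave 83-85%).

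| Unstented rate p | (1 - p)^30 | × 0.833 | Simulated |
|---|---|---|---|
| 0% | 1.00 | 83% | 83-85% |
| 1% | 0.740 | 62% | 61-63% |
| 2% | 0.545 | 45% | 45-46% |
| 4.5% | 0.248 | 21% | about 20% |

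The 4.5% is 12/264, from the 252/264 technical successes in Protocol Appendix 24.1. At that rate 30 × 12/264 = 1.4 unstented patients are expected, and the chance of at least one is 1 - 0.248 = 75%.

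**4. One stented failure, by censoring date.** The middle columns use 29 resolved patients at gamma quantiles (mean 2.35, SD 2) and one failure. The last column is simulated success with exactly one failure and times in whole days.

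| Censoring day | Mean | Upper bound | Success |
|---|---|---|---|
| 2 | 2.41 | 3.13 | about 78% |
| 7 | 2.55 | 3.35 | about 66% |
| 14 | 2.74 | 3.76 | about 29% |
| 30 | 3.27 | 5.18 | 0% |
| 60 | 4.27 | 8.04 | 0% |

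With gamma, lognormal and zero-truncated normal times the success ranges are 78-83% on day 2, 65-71% on day 7, 16-33% on day 14 and 0% on day 30.

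**5. Stented failure rates, no unstented patients** (n = 30, gamma).

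| Stented failure rate | Censored over days 0-3 | Censored on day 30 |
|---|---|---|
| 1% | 82% | 61% |
| 2% | 82% | 46% |
| 4.5% | 79% | 21% |

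The day-30 column nearly matches the unstented results in step 3.

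**6. The day-60 rerun.** It moves every earlier censoring time to day 60. By step 2, one censored patient of any kind gives a bound of at least 5.85. It therefore returns the same answer, fail, whether the primary result was secure or marginal.

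**7. The missing date.** Protocol 4.4 allows the stent to stay in indefinitely. An unresolved patient who keeps it and completes follow-up meets none of the four censoring dates. The end-of-study visit is 90 ± 14 days after placement (Protocol 7.4). Censoring at day 90 in the setting of step 4 gives mean 5.27 and bound 10.94, against 4.27 and 8.04 for an unstented patient.

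**The case against.** The strongest reply is that the plan already handles this. The protocol's revision history shows that the day-60 rule for unstented patients and the day-60 rerun came in together after regulatory feedback, so the pair is deliberate. The unstented rule works against the sponsor and cannot produce a false claim of success. The rerun is stricter than any tipping-point analysis. The 82% is correct for its stated inputs, and restating it changes neither the sample size nor the decision rule.

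Most of this stands as a defence of the primary rule. It does not rescue the power figure, which the planned analysis delivers only if nobody fails. Nor does strictness make the rerun informative, because one censored patient settles it.

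A reader might infer that early censoring biases the test towards the device and inflates false positives. The documents give no rate of early death, surgery or loss before resolution, so any such figure would rest on assumed losses. The direction is also mixed: early censoring helps the device, while day 60 counts heavily against it.

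A reader might also infer that stented failures must move to day 60 in the primary analysis. The documents do not require that. The result is already planned as a sensitivity analysis. Making it primary is a trade-off: with 3.2% stented failures ((252 - 244)/252, approximate) and no unstented patients, success is 32%, against 79% if those failures are censored on day 2. Scoring every removal before resolution as failure would also misclassify a patient whose stent is replaced at a re-intervention visit and who then resolves.

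**Conclusion.** The point holds as a mismatch between the stated power and the planned analysis, together with a sensitivity analysis that cannot grade robustness. It is not an arithmetic error, and it does not show that the primary rule is invalid. It should be fixed before the primary analysis.

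That one unstented patient fails the test follows from the SAP formulas for 30 patients and needs no distributional assumption. The success percentages assume gamma times with the plan's mean and SD. The 4.5% rate is approximate: the appendix footnote says that 21 patients appear in two of the pooled studies, technical failure is assumed to mean unstented, and Protocol 7.4 allows a second placement attempt. The 1% and 2% rows show that the conclusion does not depend on 4.5%.

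The contrast between stented and unstented failures is mainly for early death, cholecystectomy or early removal. Removal on days 30-60 weighs about as much as an unstented failure.

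**What to change.** 1. In SAP 3.1.2, restate power under the Kaplan-Meier analysis of SAP 3.1.3 for stated rates of unstented and stented failures (for example 0%, 1%, 2% and 4.5%, with the assumed censoring dates). Say that 82% applies only with no failures.
2. In SAP 3.1.3, beside the day-60 rerun, add a tipping-point analysis. It moves the censoring time of each stented patient who never resolved step by step up to day 60 and reports where the bound crosses 3.5 days. SAP 3.2.3 already plans this kind of analysis for the secondary endpoint.
3. In SAP 3.1.3, give an unresolved patient who keeps the stent and completes follow-up a censoring date, capped at day 60 so that this patient does not outweigh an unstented failure. At 30 patients the test already fails at day 60, so the cap affects the reported mean and bound, not the outcome.

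The current primary censoring rule can stay. No new data are needed. The cost is a less favourable power statement and a little more analysis work.

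### The primary 97.5% bound has no small-sample correction: with normal, uncensored times its one-sided error is 3.19% at n=30 (3.27% at n=27), not 2.5%, and the stated power points to a t test

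*SAP*

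**What the plan says.** SAP 3.1.3 estimates the mean time to resolution as the area under the Kaplan-Meier curve up to the longest observed time. Its variance is a Greenwood-type sum with terms d/[Y(Y-d)]. The "upper bound of the confidence interval of the mean will be calculated as" the estimated mean plus the normal quantile times the square root of that variance. The same section makes this the pass/fail rule: "The estimated mean and standard error from the Kaplan-Meier analysis will be used to construct a one-sided" 97.5% upper bound, and the null is rejected if the bound lies below 3.5 days.

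SAP 3.1.2 plans for the same test at one-sided alpha 0.025 and 82% power: "Expected AXIOS™ stent (test) mean days to clinical resolution = 2.35 days with standard deviation 2 days", "Evaluable number of patients needed = 27", "Expected rate of attrition = 10"%, 30 enrolled. It does not name the test behind the power figure.

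Protocol 8.1 has alpha 0.022 and 80.4% power with the same mean, SD, goal and sample size. It says that the mean and standard error "will be used to construct a one-sided 97.8% upper confidence bound of the mean", but gives no formula. The SAP takes precedence: "This SAP shall be following where there are any differences between the Statistical Methods in the protocol and this SAP". So the SAP formula is the only one on record.

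For a patient who receives no stent, SAP 3.1.3 says "the patient will be considered a failure for the endpoint with censoring at 60 days".

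**The concern.** The printed formula is a large-sample one, applied to about 30 patients. If it carries no small-sample correction, the bound labelled 97.5% covers less than that, and the test rejects a true null more often than 2.5% of the time. This bound is the primary success criterion of a single-arm study, and also the interval that would be reported. If the power was worked out for a t test, the plan has been sized with one test and will be analysed with another.

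**Working it through.** **Inputs.** From SAP 3.1.2: expected mean 2.35, SD 2, goal 3.5 (difference 1.15), one-sided alpha 0.025, n=27 evaluable and 30 enrolled. From protocol 8.1: alpha 0.022, power 80.4%. From SAP 3.1.3: the variance and bound formulas.

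**1. Reproduce the stated power.** At n=27 the noncentrality is 1.15/2 x sqrt(27) = 2.988.

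| Test | alpha 0.025 (SAP states 82%) | alpha 0.022 (protocol states 80.4%) |
|---|---|---|
| One-sample t, 26 df | 82.0% | 80.4% |
| Normal test, SD known | 84.8% | 83.5% |
| SAP rule as printed | 85.2% | 84.0% |

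Both stated figures match the t test and neither matches the other two rows.

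**2. Reduce the printed variance.** With nobody censored, the Kaplan-Meier mean is the sample mean and the variance sum equals sum((x - mean)^2)/n^2, that is, the divisor-n variance over n. This was checked numerically with and without tied times. (When the largest time is an event, the last term is 0/0 and was set to 0.)

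**3. Error of the printed rule.** At a true mean of 3.5, with normal and uncensored times, the rule rejects when T(n-1) < -1.96 x sqrt((n-1)/n).

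| | n=30 | n=27 |
|---|---|---|
| Cut-off 1.96 x sqrt((n-1)/n) | 1.927 | 1.923 |
| t quantile (0.975, n-1 df) | 2.045 | 2.056 |
| Ratio of half-widths | 0.942 (5.8% short) | 0.936 (6.4% short) |
| One-sided error, SAP rule | 3.19% | 3.27% |
| Error with the normal quantile and divisor n-1 | 2.98% | 3.04% |

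Most of the excess comes from the normal quantile, and the missing n/(n-1) adds the rest. The n=30 column is the more relevant one, because all ITT patients are analysed and unresolved patients are censored rather than dropped.

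**4. Size in days.** At a sample SD of 2 the half-width is 0.704 against 0.747 days (n=30), and 0.740 against 0.791 (n=27). The decision differs only for an observed mean of about 2.75 to 2.80 (n=30) or 2.71 to 2.76 (n=27).

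**5. Early loss.** The plan expects 10% attrition. With up to 3 of 30 patients lost at random times over days 0-1, 0-3.5 or 0-7, and normal or uniform resolution times, the simulated error is about 3.2-3.5%.

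**6. Skewed times (shape assumed, SD 2 kept at a mean of 3.5).** Gamma times give 5.4% (n=30) and 5.7% (n=27). Negative binomial times give 4.4% and 4.5%. The documents fix neither the shape nor the SD at that mean.

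**7. Patients at 60 days.** If one patient is last at 60 days and all others resolve on day 0, the bound is (60/n)(1 + 1.96 x sqrt((n-1)/n)). This is 5.85 days (n=30) or 6.50 (n=27), so the test cannot pass. The figures in step 3 therefore describe only trials without such a patient.

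**The case against.** **The effect is small, and normality is an assumption.** Both stand. With whole-day times and a sample SD of 2, the two rules disagree for a single attainable total: 83 days at n=30, 74 at n=27. Study success also requires the secondary null to be rejected. Normality is not an unfavourable choice, however, since the right-skewed cases in step 6 give larger errors.

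**The mismatch between tests is inferred.** This stands, since SAP 3.1.2 names no test. Nor does a mismatch mean that the trial is undersized: if power was computed with t, it understates the power of the printed rule.

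**A reader might infer that the study-wide error is below 2.5%, because one 60-day patient blocks success.** The argument would multiply the chance of having no such patient by 3.2%. That product places the mean of 3.5 only on the patients not at 60 days. The hypothesis in SAP 3.1.1 concerns the mean for study patients, and SAP 3.1.3 evaluates all ITT patients. Suppose the placement rates in the protocol appendices held (252/264 or 141/146; the first counts some patients twice, by its own footnote).

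- An ITT mean of 3.5 over 60 days leaves the others averaging (3.5 - 60 x 12/264)/(252/264) = 0.81 days, or (3.5 - 60 x 5/146)/(141/146) = 1.50 days.
- Trials with no 60-day patient then almost always pass. Their share is 0.9545^30 = 25% to 0.9658^30 = 35% at n=30, and 28% to 39% at n=27.
- Simulated overall error is about 25-39% (gamma times, SD 0.5 to 2 assumed), and the t correction changes it by at most about 0.3 points.

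So the 60-day rule does not make the test conservative. Where such patients are possible, it governs the overall error, and the present point is minor beside it.

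**Conclusion.** The point holds as a small-sample defect in a printed formula. For normal, uncensored times the primary bound has a one-sided error of 3.19% (n=30) or 3.27% (n=27) instead of 2.5%, and covers the true mean 96.8% or 96.7% of the time instead of 97.5%. With early loss of up to 3 of 30 the error is about 3.2-3.5%. The algebra is certain, while the rates rest on the assumed normal shape and on no patient being censored late. That planning used a t test is a strong inference from two matching power figures, not something the documents state.

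These figures are not the error rate of the whole study, and the documents do not support reading them as such in either direction. The practical effect is 0.04 to 0.05 days at a sample SD of 2. It is worth correcting before analysis because the change is one formula and brings the analysis into line with the stated power.

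**What to change.** In SAP 3.1.3, replace the normal quantile by the t quantile with m-1 degrees of freedom and multiply the variance by m/(m-1), where m is the number of observed resolutions (m=n if nobody is censored). State that the program must follow this formula. In SAP 3.1.2, name the one-sample t test as the basis of the power.

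For normal, uncensored data this gives 2.5% error and the stated 82% power at n=27. With up to 3 of 30 lost early, the simulated error is about 2.5-2.7%.

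**Cost.** No patients and no data. Power falls by two to three points relative to the printed rule: 86.1% against 88.5% at n=30, and 82.0% against 85.2% at n=27.

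**Limits.** The change corrects the small-sample error only. In the assumed right-skewed cases with SD 2, about 3.6-4.7% remains, so a skewness-robust bound could be added as a supporting analysis; this is optional. The change does nothing about the effect of censoring no-stent patients at 60 days, which needs separate attention.
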